9.6. Safety Oversight (ISM plus SMC or DSMB)

Independent safety oversight will be under the direction of a DSMB composed of individuals with expertise in clinical pediatrics, schistosomiasis, biostatistics, and clinical trials methodology. The DSMB will be engaged until the last patient is enrolled and treated at baseline. We expect this will be about 18-24 months. An independent safety monitor (ISM) will be identified in Uganda and The Philippines. The individuals will be physicians, independent of the trial, and live in close proximity to the study activities. The DSMB will operate under the rules of an IRB-approved charter that will be written at the organizational meeting of the DSMB. The DSMB will set the frequency of planned meetings and establish safety criteria for additional ad hoc meetings. The DSMB will advise PIs and IRBs of its findings. The DSMB had a first meeting to review the protocol and develop the charter on June 14, 2019. DSMB suggestions for changes to the protocol are reflected in this protocol.

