| US | United States |
| UVRI | Uganda Virus Research Institute |
| WHO | World Health Organization |

Protocol Summary

| | |
|---------------------------------------|--|
| Title: | Praziquantel for children under four: A Phase II PK/PD driven dose finding trial |
| Phase: | 2 |
| Population: | 
Sample size N=600
 
Sex: Male:Female (1:1)
 
Ages: 12 – 47 months old inclusive
 |
| Number of Sites: | Two: Uganda (N=300) and Philippines (N=300) |
| Study Duration: | 36 months |
| Duration of Subject participation | 13 months |
| Description of Agent or Intervention: | 
Baseline: Children will receive either
 
1-Praziquantel 40 mg/kg given as a single dose and placebo 3 hours later
 
or
 
2-Praziquantel 80 mg/kg (40 mg/kg followed by 40 mg/kg 3 hours later)
 
Six months post baseline: Praziquantel given at the child's baseline dose or placebo
 
Oral route – crushed tablets
 
12 months post baseline: Praziquantel only to children positive by any diagnostic test at same baseline dose.
 |
| Objectives: | 
Primary:
 
 To assess parasitologic cure and egg reduction rate of praziquantel (PZQ) at two different doses (40 mg/kg or 80 mg/kg split as two doses over three hours) among children aged 12-47 months. |

[figure not shown]
| | |
|-------------------|--|

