Study Arms: The study will have four arms as follows:

Arm 1: 40 mg/kg dose at baseline & Placebo 3 hours later//Placebo & Placebo 3 hours later at six months post baseline (N = 150). N=75 will be recruited in this arm at each site.

Arm 2: 40 mg/kg dose at baseline & Placebo 3 hours later //40 mg/kg dose & Placebo 3 hours later at six months post baseline (N = 150). N=75 will be recruited in this arm at each site.

Arm 3: 80 mg/kg dose split at baseline as 40 mg/kg and 40 mg/kg 3 hours later// Placebo & Placebo 3 hours later at six months post baseline (N = 150). N=75 will be recruited in this arm at each site.

Arm 4: 80 mg/kg dose at baseline split as 40 mg/kg and 40 mg/kg 3 hours later //80 mg/kg dose split as 40 mg/kg and 40 mg/kg 3 hours later at six months post baseline (N = 150). N=75 will be recruited in this arm at each site.

Study Enrollment timeline: Subject screening and recruitment will occur over 24 months.

Duration of participation: Individual subject participation will be approximately 13 months

Study agent and administration: For study agent conformity and quality, we will obtain PZQ tablets from a single source, Macleods Pharmaceuticals. Children will be randomized and receive either 40 mg/kg or 80 mg/kg (split as 2 doses of 40 mg/kg over 3 hours) at baseline. Children randomized to the 40 mg/kg arm will receive placebo 3 hours post treatment while children randomized to the 80 mg/kg arm will receive two split doses of 40 mg/kg over 3 hours. At the six months post initial treatment time point, children will be randomized to receive the same dose as they received at baseline or to receive placebo. The research pharmacy, *Tedor Pharma, Cumberland, RI*, will compound a placebo tablet matched for the active agent's excipients, color, shape, and size.

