3. *Study Visit 3 (6 months post enrolment)* Six months (+/- 2 weeks) following visit one, subjects will return to the respective field laboratories. They will receive either the same dose of Praziquantel as received at Visit 1 or placebo as determined at baseline randomization. At this

visit, and before the study drug or placebo is received, blood will be drawn for follow up assessment of morbidity, and in depth measures of nutritional status. An ultrasound scan will be performed. Blood (7 ml) will be collected for the same subset of N=150 subjects for studies of immunological responses. Urine will be stored at this visit for future processing of CAA to monitor re-infection.

4. Study Visit 4, Close out. (12 months post enrollment) Twelve months (+/- 2 weeks) post enrollment and initial treatment, study subjects will return to the field laboratory. Prior to this visit they will be asked to provide three stool samples and one urine. At this visit, blood will be drawn for follow up morbidity studies and in-depth measures of nutritional status will be made. All children will be treated with Praziquantel and those infected with soil-transmitted helminths will be treated with albendazole 200 mg (12 – 24 month old children) or albendazole 400 mg (children over age two). A repeat ultrasound scan will be done before the participant is discharged from the study. If however, the ultrasound scan at six months revealed resolution of any pathology detected at baseline, there will be no repeat at discharge. Blood (7 ml) will be collected for the same subset of N=150 subjects for studies of immunological responses.

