9.5. Halting Rules

Safety findings that would lead to temporary suspension of enrolment include:

- 1) A greater than expected number of total serious adverse events deemed associated with the study product as defined by two or more SAEs associated with the study product among the first 20 children enrolled and then five or more serious adverse events among children, associated with the intervention per 100 children enrolled (5%).
- 2) 15 subjects per 100 enrolled experiencing adverse drug events as defined by a) an unexpected adverse event, as defined by a clinical adverse event (not a laboratory defined adverse event) that is not listed as expected with treatment, that occurs within 2 days after dosing, If the total number of unexpected adverse drug events occurs among 15 children per 100 enrolled or 15% or more of children, halting rules would apply.

If either of the above occurs, this would lead to temporary suspension of enrolment and a safety review (either routine or ad hoc), the objective of which is a decision as to whether the study (or intervention for an individual or study cohort) should continue per protocol, proceed with caution, be further investigated, be discontinued, or be modified and then proceed. Suspension of enrollment (for a particular group or for the entire study) is another potential outcome of a safety review.

Subsequent review of serious, unexpected, and related AEs by the Medical Monitor, DSMB, IEC/IRB, the sponsor(s), or relevant local regulatory authorities may also result in suspension of further trial interventions/administration of study product at a site. The study sponsor(s) retain the authority to suspend additional enrollment and study interventions/administration of study product for the entire study, as applicable.

Individual Halting Rules

A child will be discontinued from the study if he/she experiences a severe allergic/anaphylactic reaction to any dose of Praziquantel given during the study (enrolment or six months).

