9.6.2. Data and Safety Monitoring Board (DSMB)

Safety oversight will be conducted by a DSMB that is an independent group of experts that monitors subject safety and advises the PIs and study staff. The DSMB members will be separate and independent of study personnel participating in this trial and should not have scientific, financial or other conflict of interest related to this trial. The DSMB will consist of members with appropriate expertise to contribute to the interpretation of the data from this trial.

The DSMB will operate under the rules of an approved charter that will be written and agreed upon at the organizational meeting of the DSMB. Procedures for DSMB reviews/meetings will be defined in the charter. Reports may include enrolment and demographic information, medical

history, concomitant medications, physical assessments, clinical laboratory values, dosing compliance, and solicited and unsolicited AE/SAEs. The DSMB will review SAEs on a regular basis and ad hoc during this trial. The Medical Monitor and the ISM (as deemed necessary) will be responsible for reviewing SAEs in real time.

The DSMB will conduct the following reviews:

- Interim analysis
- Ad hoc when a halting rule is met: DSMB chair may convene an ad hoc meeting if there are immediate concerns regarding observations during the course of this trial.
- Final review meeting: 6 to 8 months after clinical database lock to review the cumulative unblinded safety and efficacy data for this trial. The data will be provided in a standard summary format. The DSMB may be asked to provide recommendations in response to questions posed by PIs.

Additional data may be requested by the DSMB, and interim statistical reports may be generated as deemed necessary and appropriate by PIs or other study staff. The DSMB may receive data in aggregate and presented by treatment arm. The DSMB may also be provided with expected and observed rates of the expected AEs in an unblinded fashion, and may request the treatment assignment be unblinded for an individual subject if required for safety assessment. The DSMB will review grouped and unblinded data in the closed session only. As an outcome of each review/meeting, the DSMB will make a recommendation as to the advisability of proceeding with study procedures and to continue, modify, or terminate this trial.

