11.3. Planned Interim Analyses

11.3.1. Interim Safety Review

Given that the study population is vulnerable the project will require rigorous independent oversight by a data safety and monitoring board (DSMB). DSMB membership will be independent of the trial with input from investigators; we anticipate that it will comprise experts on schistosomiasis and child health, and a statistician with experience of trials in LMICs. The frequency of meetings and other procedural issues will be overseen by the study sponsor.

The DSMB will regularly monitor all data to consider any potential harm to participants. Formal rules for stopping due to harm will be discussed with the DSMB at their first meeting. An interim analysis will be performed on the primary outcome when approximately 20% of children have been randomised. Only the DSMB and the trial statistician will be unblinded for this interim analysis.

The DSMB will meet once three months after study enrollment begins and then every six months during enrollment.

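### DSMB engagement and meetings are tied to enrolment in Sections 9.6, 11.3.1 and 15.4 but run through and beyond the trial in 9.6.2, so by-arm review of later dosing is unsettled

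*Combined protocol and SAP*

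**What the plan says.** Section 9.6 fixes when the board stops: "The DSMB will be engaged until the last patient is enrolled and treated at baseline". It adds: "We expect this will be about 18-24 months". Section 11.3.1 sets the calendar: "The DSMB will meet once three months after study enrollment begins and then every six months during enrollment". Section 15.4 repeats that sentence. On enrolment, Section 4.2.1 states: "Subject screening and recruitment will occur over 24 months". The Protocol Summary gives a study duration of 36 months.

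Dosing continues after a child's baseline visit. For Study Visit 3, six months later, Section 4.2.1 says of the children: "They will receive either the same dose of Praziquantel as received at Visit 1 or placebo as determined at baseline randomization". Table 1 shows active drug at that visit in Arms 2 and 4, and only Arm 4 receives a second 80 mg/kg course. Praziquantel is given again at month 12. The Protocol Summary and Section 7.6 limit this to test-positive children, whereas Section 4.2.1 (Study Visit 4) and Section 7.7 give it to all.

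Section 9.6.2 describes a longer-lived board. It reviews SAEs regularly and ad hoc over the course of the trial, can be convened when a halting rule is met, and holds this review: "Final review meeting: 6 to 8 months after clinical database lock to review the cumulative unblinded safety and efficacy data". Section 15.4 also mentions six-monthly reviews of outcomes by the board, in a sentence that carries no enrolment limit.

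Section 9.5 says what a trigger does: "If either of the above occurs, this would lead to temporary suspension of enrolment and a safety review". The review then decides whether the study, or the intervention for an individual or cohort, continues, changes or stops. The same section allows study product to be suspended at a site after later review, and allows the sponsor to suspend it study-wide.

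**The concern.** A board whose engagement ended with the last baseline dose cannot also convene on a later trigger or hold a review after database lock. The sections cannot all be followed as written.

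The difference matters because repeat 80 mg/kg dosing occurs only at month 6, and part of it falls after enrolment closes. A comparison of safety by arm is what a DSMB sees and others do not: the independent safety monitor in Section 9.6.1 evaluates individual SAEs and is not assigned by-arm review. Even if Section 9.6.2 prevails, its only fixed review after enrolment comes after database lock, when no dose can be affected.

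Section 9.5 leaves a related gap. The pause that follows a trigger automatically is a pause of enrolment. Once enrolment has closed there is nothing for it to suspend, and while enrolment is open the text does not say whether pending month-6 doses wait for the review. The individual rule in the same section names the six-month dose; the group rules do not.

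**Working it through.** **Inputs from the protocol.** N = 600 and study duration 36 months (Protocol Summary). Enrolment T = 24 months (Protocol Summary, Section 4.2.1), with 18 months as the lower end of the DSMB period expected in Section 9.6. Dosing visits at 6 and 12 months, each ± 2 weeks (Section 4.2.1). Half the cohort is on active drug at month 6 (Section 4.1). Meetings at month 3 and then six-monthly during enrolment (Section 11.3.1), which gives months 3, 9, 15 and 21 if T = 24, and 3, 9 and 15 if T = 18.

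**Assumption.** The documents give no accrual curve. Uniform accrual is the base case; linearly rising and falling accrual give a range. Attrition is ignored.

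**The plan's own figure.** 24 months of enrolment + 12 months to the last visit = 36 months, matching the stated duration (37 if the stated 13-month participation is used). The 18–24 months in Section 9.6 therefore matches enrolment, not the study.

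**Visits after the last baseline dose.** Under uniform accrual the share of month-m visits falling after month T is m/T.

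| Visit | T = 24 | T = 18 |
|---|---|---|
| Month 6 | 6/24 = 25%, 150 of 600 | 6/18 = 33%, 200 of 600 |
| Month 12 | 12/24 = 50%, 300 of 600 | 12/18 = 67%, 400 of 600 |

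Of the 300 active month-6 courses, 75 (T = 24) to 100 (T = 18) come after engagement ends. Half of those, about 37 to 50, are in Arm 4. Using the edges of the visit window, the month-6 share is 23% to 36% and the month-12 share 48% to 69%.

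**Visits after the last scheduled meeting.** Children enrolled within m months of that meeting, or later, have their month-m visit after it.

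- T = 24, last meeting month 21. Month 6: 1 − 15/24 = 37.5% (225 children). Month 12: 1 − 9/24 = 62.5% (375).
- T = 18, last meeting month 15. Month 6: 1 − 9/18 = 50% (300). Month 12: 1 − 3/18 = 83% (500).

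**Accrual shape, after the last baseline dose.** With linearly falling accrual the share is (m/T)²; with linearly rising accrual it is 1 − ((T − m)/T)².

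| Visit and enrolment period | Falling | Rising |
|---|---|---|
| Month 6, T = 24 | 6% | 44% |
| Month 6, T = 18 | 11% | 56% |
| Month 12, T = 24 | 25% | 75% |
| Month 12, T = 18 | 44% | 89% |

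The size depends heavily on accrual, but it is not zero: a child enrolled in the last six months has the month-6 visit after the last baseline dose, apart from small shifts within the visit window.

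**Visits and doses.** At month 6 every child receives active drug or placebo, so visits equal blinded administrations. At month 12 the number of doses cannot be derived, because the sections disagree on who is treated.

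**The case against.** A reader might infer that these doses have no DSMB oversight, that most month-12 doses are affected, and that a halt can stop nothing but enrolment. The documents do not support any of these.

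- **No DSMB oversight.** This takes Section 9.6 as settled. Section 9.6.2 gives the board SAE and ad hoc review through the trial, and Section 15.4 has a sentence on six-monthly reviews without an enrolment limit. Section 9.6 lets the board set its meeting frequency, under a charter that is not among these documents. What is shown is an unreconciled contradiction.
- **Most month-12 doses.** At the stated 24-month enrolment the share is exactly half of visits under uniform accrual, and the number of doses is unknown. Whether month-12 treatment counts as study drug is also unclear: the Protocol Summary places interventions at baseline and 6 months, and the vials in Section 4.2.1 cover only those visits.
- **A halt stops only enrolment.** Section 9.5 also requires a safety review and allows study product to be suspended. Those powers are discretionary; only the automatic step is limited to enrolment.
- **Other oversight.** The independent safety monitor serves throughout, with real-time record access (Section 9.6.1). The Medical Monitor reviews SAEs in real time (Section 9.6.2). Halting reports go to trial staff and sponsor (Section 15.4).
- **Halting counts.** Counting per children enrolled does not exclude month-6 events, since enrolled children stay in the count.
- **Most repeat dosing is covered.** With 24-month uniform accrual, 75% of month-6 dosing, about 112 of Arm 4's 150 repeat courses, occurs while the board is engaged even on Section 9.6's terms.

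All of this stands and limits the point. It does not resolve the conflict over how long the board serves, and it does not supply a routine by-arm meeting with a fixed date between the end of enrolment and database lock.

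**Conclusion.** The point holds as an internal contradiction with a safety consequence. Sections 9.6, 11.3.1 and 15.4 tie engagement and scheduled meetings to enrolment; Section 9.6.2, and one sentence of 15.4, do not. On Section 9.6's terms 25% to 33% of month-6 visits and 50% to 67% of month-12 visits follow the end of engagement, and 37.5% to 50% of month-6 visits follow the last scheduled meeting. These figures assume uniform accrual over 24 or 18 months. Other accrual shapes move the month-6 share after engagement ends to between about 6% and 56%.

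On halting, the supportable statement is narrow: the automatic action names suspension of enrolment and a review, suspension of study product is possible but discretionary, and the text is silent on whether the automatic pause reaches follow-up dosing. The documents do not show that later doses go unsupervised.

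**What to change.** Reconcile Sections 9.6, 11.3.1 and 15.4 with Section 9.6.2, and carry the result into the DSMB charter, so that engagement and the six-monthly meetings run until the last study-drug dose and its safety follow-up are complete. State whether month-12 treatment counts as study drug for this purpose, and reconcile the sections that disagree on who receives it.

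In Section 9.5 the sponsor and DSMB should state whether a triggered halt, and the counts per 100 enrolled, apply to the month-6 and month-12 administrations. No particular stopping rule is proposed here.

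The cost is wording plus about one or two meetings of a board that already exists. With 24-month enrolment the six-monthly calendar continues at month 27, and at month 33 if month 12 is included (last visits at months 30 and 36). With 18-month enrolment the extra meetings are at month 21, and month 27 if month 12 is included (last visits at months 24 and 30). Engagement through the last month-12 visit would run about 36 months, or 30 with 18-month enrolment, instead of 18 to 24.

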9.6.1. Independent Safety Monitor (ISM)

The ISM will be a physician with relevant expertise whose primary responsibility will be to provide to the PI and DSMB an independent safety assessment in a timely fashion. Participation is for the duration of the study and is a voluntary position that does not receive payment. The ISM will meet the requirements of the NIH conflict of interest policy.

The ISM:

- Is in close proximity to the study site and has the authority and ability to readily access study participant records in real time.

- May be a member of the participating institution's staff but preferably be from a different organizational group within the institution.
- Will not be in a direct supervisory relationship with the investigator.
- Will have no direct involvement in the conduct of the study.

The ISM will:

- Sign a Conflict of Interest (COI) certification at the time they are asked to participate and provide updates to this information as needed.
- Receive reports of Serious Adverse Events (SAEs) from the site investigator and will be notified by email when the PI is notified of the SAE.
- Evaluate the SAE and report their clinical assessment to the PIs, through in a timely manner using the attached report form and email the report.
- Communicate with the investigator at the participating site as needed.
- Review additional safety related events at the request of NIH.
- Provide additional information to the PIs and/or the DSMB by teleconference as requested.

9.6.2. Data and Safety Monitoring Board (DSMB)

Safety oversight will be conducted by a DSMB that is an independent group of experts that monitors subject safety and advises the PIs and study staff. The DSMB members will be separate and independent of study personnel participating in this trial and should not have scientific, financial or other conflict of interest related to this trial. The DSMB will consist of members with appropriate expertise to contribute to the interpretation of the data from this trial.

The DSMB will operate under the rules of an approved charter that will be written and agreed upon at the organizational meeting of the DSMB. Procedures for DSMB reviews/meetings will be defined in the charter. Reports may include enrolment and demographic information, medical

history, concomitant medications, physical assessments, clinical laboratory values, dosing compliance, and solicited and unsolicited AE/SAEs. The DSMB will review SAEs on a regular basis and ad hoc during this trial. The Medical Monitor and the ISM (as deemed necessary) will be responsible for reviewing SAEs in real time.

The DSMB will conduct the following reviews:

- Interim analysis
- Ad hoc when a halting rule is met: DSMB chair may convene an ad hoc meeting if there are immediate concerns regarding observations during the course of this trial.
- Final review meeting: 6 to 8 months after clinical database lock to review the cumulative unblinded safety and efficacy data for this trial. The data will be provided in a standard summary format. The DSMB may be asked to provide recommendations in response to questions posed by PIs.

Additional data may be requested by the DSMB, and interim statistical reports may be generated as deemed necessary and appropriate by PIs or other study staff. The DSMB may receive data in aggregate and presented by treatment arm. The DSMB may also be provided with expected and observed rates of the expected AEs in an unblinded fashion, and may request the treatment assignment be unblinded for an individual subject if required for safety assessment. The DSMB will review grouped and unblinded data in the closed session only. As an outcome of each review/meeting, the DSMB will make a recommendation as to the advisability of proceeding with study procedures and to continue, modify, or terminate this trial.

